7. RESEARCH QUESTION AND OBJECTIVES

The aim of this study is to describe the clinical characteristics and outcomes of patients with ATTR amyloidoid cardiomyopathy (ATTR-CM) treated with tafamidis at a single center in Turkey.

Primary Objective:

- To describe the rate of hospitalizations and emergency admissions due to chronic heart failure in the patients treated with Tafamidis

Secondary Objectives:

- To describe the rate of cardiovascular-related hospitalizations and overall survival among patients treated with Tafamidis during Tafamidis exposure time period.
- To describe the presence of cardiac and extracardiac red flags (Extra-cardiac Red Flags: Carpal Tunnel Syndrome, Peripheral Neuropathy, Lumbar Stenosis, Renal Insufficiency, Cardiac Red

Flags: Elevated NT Pro BNP and troponin, Pseudo infarct Sign, Voltage Mismatch, Conduction Disorder, Increased Wall Thickness (Interventricular septum), Pericardial Effusion)) in patients with ATTR - CM treated with tafamidis during the baseline period prior to initiation of tafamidis treatment.

- To describe the clinical and functional outcomes in ATTR CM patients during the baseline period prior to tafamidis treatment and during the follow-up period of treatment with tafamidis such as HRQoL measures, concomitant medication, biomarkers (NT pro-BNP, troponin), echocardiographic parameters (6 min walk test, Kansas City Cardiomyopathy Questionnaire Score, Creatinine eGFR, Ejection Fraction, Interventricular Septum, E/A ratio, E/e' mean ratio, Tricuspid Regurgitation Velocity, Tricuspid Annular Plane Systolic Excursion).

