8. RESEARCH METHODS

8.1. Study Design

This is a single-center, retrospective, non-interventional cohort (Figure 1) study. Pseudonymized data will be entered in CRF from individual patient medical records maintained in a single center in Turkey according to clinical practice. Data will be collected using electronic case report form (eCRF). Subjects include diagnosed with ATTR-CM in the January 2023 – January 2025 and treated with tafamidis. For all patients, the 6-month period before the index date when tafamidis is started will be considered as the baseline period, and the relevant parameters will be collected from this period. From the start of tafamidis, quarterly follow up of the patients is defined as treatment period and clinical and functional outcomes, hospitalization and emergency admission due to CHF, CV related hospitalizations and mortality data will be obtained from this treatment period. Tafamidis treatment discontinuation is defined as interrupting the treatment for at least 10 days or completely stopping it, which will be determined by the primary investigator from the EHR records (Electronic Health Record). Hospitalization and emergency admission due to CHF (Chronic Heart Failure) and CV (Cardiovascular) related hospitalizations and other variables are described in Section 9.3.1. and Table 1.

[figure not shown]

Figure 1. Study diagram

Rationale for the study design. The rationale for choosing a retrospective cohort design is that the data points of interest outlined in the study protocol are routinely collected in the Turkish clinical practice. Therefore, the retrospective approach will ensure that the dataset is available on the site. The single center participating in the study is highly specialized and skilled in the management of the target population.

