8.2. Setting

One Turkish Centre involved in the diagnosis and management of patients affected by ATTR-CM will participate in the study. This Centre is selected according to their clinical and research expertise, in

addition to the number of patients they are used to routinely caring for. A clinical research organization (CRO) on behalf of Pfizer will support the regulatory and administrative procedures to get authorization and the operations at Centre needed for data collection.

After regulatory authorization and local contract finalization, the study will be started at Centre. The site Study Team, including the Principal Investigator and additional identified personnel (e.g., research nurse, clinical study manager) will be trained on the protocol and planned study procedures, in addition to the use of the study-specific eCRF. Study data will be collected according to [Section 9.1. Study Design](#) and [Figure 1](#) as patients are diagnosed with ATTR-CM between January 2023 and January 2025. For all patients, the 6-month period before the index date when tafamidis is started will be considered as the baseline period, and the relevant parameters will be collected from this period. Original data, routinely collected by means of specific tools (e.g., paper charts, electronic charts,) will be transferred to the eCRF by the Study Team in site.

Retrospective data from the patient's files/source data will be collected in the CRF up to the earliest date of: treatment discontinuation, death, lost to follow-up (the patient could not be observed and any more contacted at some time point during their follow-up) or end of the follow-up period of 30-Sep-2025 (inclusive). For the patients lost to follow-up, the end of their follow-up period will be the respective date of the last contact. In the case patients experience clinical events (e.g. hospitalization due to Chronic Heart Failure, safety event) starting before 30-Sep-2025 and continuing beyond end of the follow-up, the respective details until the end of the event should be included into the eCRF.

The CRO will ensure oversight and monitoring of the study at the site.

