Tafamidis treatment end date	Primary and secondary objective	Follow up assessment period	Continuous	Electronic health records or physical patient file	Electronic health records or physical patient file	The date on which a patient stops receiving Tafamidis treatment, recorded in the patient's medical records. (DD/MM/YYYY)

Any discontinuation of Tafamidis (Yes/No)	Primary and secondary objective	Follow up Assessment Period	Nominal	Electronic health records or physical patient file	The cessation of Tafamidis treatment for any reason (Yes/No)
Tafamidis discontinuation reason (1. Mortality, 2. Reimbursement rule, 3. Lost to follow up, 4. other)	Primary and secondary objective	Follow up Assessment Period	Ordinal	Electronic health records or physical patient file	Tafamidis Discontinuation Reason: (1. Mortality, 2. Reimbursement rule, 3. Lost to follow up, 4. other)

The dates of parameters obtained from tests such as ECG and echocardiography recorded at baseline, index, and follow-up dates will be entered into the eCRF system.

8.3.1. Definition of CHF-, CV - related hospitalizations and emergency admissions, and Red Flags

In our study, CHF and CV-related hospitalizations will be defined as following:

In this center and Turkish clinical practice, a **hospitalization or emergency admission due to chronic heart failure** is defined as an unplanned hospital admission due to worsening heart failure symptoms requiring intravenous diuretics, inotropic support, or other advanced heart failure therapies. In the electronic healthcare records international classification system codes (Version of ICD 10, such as I50 Heart Failure and its subcodes I50.1 Left ventricular failure, I50.2 Systolic Heart Failure, I50.3 Diastolic Heart Failure, I50.4 Combined Heart Failure, I50.8 Combined Heart Failure, etc.) for chronic heart failure hospitalization is defined and well recorded in this site. Emergency admissions for causes not related to chronic heart failure could not be accurately and completely captured; thus, these will not be recorded in CRF.

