8.6. Data Management

Data management will be performed by the CRO acting on behalf of Pfizer.

Data Collection and Entry: Patient data will be collected retrospectively from electronic health record systems maintained at the single participating center. The treatment protocol notes data will be collected in the eCRF. The data collection period is between January 2023 and September 2025. Patient data will be collected during the baseline diagnosis period and then throughout the treatment period (while the patient is under tafamidis treatment) during follow-ups period. The study does not involve any patient contact and will not impact the care patients receive. Preidentified data regarding the patients will be collected in electronic Case Report Forms eCRF and analyzed to accomplish the proposed study objectives.

Data will be collected on the e-CRF application, which will be prepared based on the CRF that will be developed specifically for this study. The e-CRF will meet the scientific, regulatory, and logistical requirements of the study before it is used to record data for this study. Before using the e-CRF, all users will receive training on the system and study specific training.

The single investigator from a single center and a site coordinator will be defined in the system. Form controls will be used for the appropriate data fields (for data fields with clear boundaries and content), this will prevent any data entry outside the limits set for the investigator. For data fields that cannot be limited by form controls but have boundaries, automatic form controls will be provided in the system.

All data required for the study, including nurses' measurements, patient demographics and necessary previous medical records will be recorded to the e-CRF manually by the investigator. The investigator is responsible for the accuracy of these manually recorded data.

During patient data entry, the faulty/missing data scan will be performed by the e-CRF automatically. In this way, any form with faulty or missing data will not be allowed to send data to e-CRF, and warning messages will be displayed on the computer screen to the person entering the data to ensure that he/she enter data correctly and completely.

Data cleaning and, if necessary, source data verification will be conducted. After cleaning, the database will be locked, and the data will be extracted in the appropriate format.

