8.7. Data Analysis

The anonymously collected data of each patient cohort will be analyzed with an exploratory data analysis approach. The de-identified dataset will be analyzed using statistical software. Descriptive

statistics, survival analyses, and exploratory methods will be employed to address study objectives. Outliers and data inconsistencies will be reviewed and addressed before final analysis. Only descriptive statistics will be reported and no effort to determine statistical significance will be made.

Hospitalization and emergency department admission rates attributable to chronic heart failure, as well as hospitalization rates for cardiovascular-related illness, will be expressed as events per patient-year to account for variable follow-up durations.

Overall survival will be described using the Kaplan–Meier method, appropriately accounting for differing follow-up times and censoring; competing risks will not be considered.

Cardiac and extra-cardiac “red flags,” together with clinical and functional outcomes, will be described using means (standard deviations) for continuous variables and proportions for categorical variables.

Missing data will not be imputed; all analyses will be based on available data, with the number of missing observations reported for each variable where applicable.

Detailed methodology for summary and statistical analyses of data collected in this study will be documented in a statistical analysis plan (SAP), which will be dated, filed, and maintained by the sponsor. The SAP may modify the plans outlined in the protocol; any major modifications of primary endpoint definitions or their analyses would be reflected in a protocol amendment.

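### Death capture ends at tafamidis discontinuation, including a 10-day interruption, so the planned Kaplan-Meier estimate is on-treatment survival rather than overall survival

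*Protocol*

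**What the plan says.** Four parts of the protocol set the window for deaths.

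- Section 8.2 collects data "up to the earliest date of: treatment discontinuation, death, lost to follow-up" or 30-Sep-2025, whichever comes first.
- Section 8.1 takes deaths from the period on drug: "CV related hospitalizations and mortality data will be obtained from this treatment period". Section 8.6 agrees, collecting data "throughout the treatment period (while the patient is under tafamidis treatment").
- Section 8.1 also sets a broad definition: "Tafamidis treatment discontinuation is defined as interrupting the treatment for at least 10 days or completely stopping it".
- Section 7 words the secondary objective as "overall survival among patients treated with Tafamidis during Tafamidis exposure time period".

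Section 8.7 then drops the exposure qualifier. It describes overall survival by Kaplan-Meier, "appropriately accounting for differing follow-up times and censoring; competing risks will not be considered".

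Table 1 in section 8.3 defines the treatment end date as "The date on which a patient stops receiving Tafamidis treatment" and describes discontinuation as cessation for any reason. Neither entry mentions the 10-day rule.

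**The concern.** A Kaplan-Meier curve estimates overall survival only if patients censored at a given time have the same later risk of death as those still followed. Here a treatment stop is itself a censoring event. Section 8.1 describes ATTR-CM as progressive, so it is plausible that a stop or a 10-day gap falls around a decline or a long admission, when risk is raised. A patient who stops and dies some weeks later enters the analysis as censored alive.

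The third inclusion criterion in section 8.2.1 admits patients who received tafamidis in the past, so the cohort can include people who have stopped. A statistical analysis plan cannot repair this, because the later deaths would never reach the eCRF.

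A second, smaller matter touches the primary rate. If a patient interrupts for 10 days or more and restarts, section 8.1 points to the interruption as the end of exposure, while Table 1 can be read as pointing to the final stop. Section 8.7 expresses the primary result as events per patient-year, so the choice changes the denominator and which events count.

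**Working it through.** The protocol states no survival rate, discontinuation rate or event count, so it has no figure to reproduce. The check has two parts.

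**1. The text.** Sections 8.1, 8.2 and 8.6 agree that capture ends with treatment. Section 7 restricts survival to exposure; section 8.7 does not. No section provides for recording a death after discontinuation, or after treatment resumes following a gap. None states the independent-censoring assumption.

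**2. An illustration of size.** All rates are assumptions, with constant hazards per year:

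- L = death hazard on treatment (0.05 to 0.10)
- G = hazard of stopping (0.05 to 0.20)
- R = ratio of the death hazard after stopping to that on treatment (2 to 5, with 1 and 0.5 as checks)
- t = 2 years

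Kaplan-Meier censored at stopping estimates exp(-L·t). Survival with deaths followed past stopping is

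exp(-(L+G)t) + G·[exp(-R·L·t) - exp(-(L+G)t)] / (L + G - R·L),

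and when L + G = R·L this becomes exp(-(L+G)t)·(1 + G·t).

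Middle case, L = 0.10, G = 0.10, R = 3:

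- Censored at stopping: exp(-0.2) = 0.819.
- Deaths followed: exp(-0.4) + 0.10 × (exp(-0.6) - exp(-0.4)) / (0.2 - 0.3) = 0.6703 + 0.10 × (0.5488 - 0.6703) / (-0.1) = 0.6703 + 0.1215 = 0.792.
- Difference: 2.7 points.

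Lowest case, L = 0.05, G = 0.05, R = 2: exp(-0.1) = 0.905 against exp(-0.2) × 1.1 = 0.901, a difference of 0.4 points.

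Highest case, L = 0.10, G = 0.20, R = 5: 0.819 against 0.5488 + 0.20 × (0.3679 - 0.5488) / (-0.2) = 0.730, a difference of 8.9 points.

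| L | G | R | Censored at stop | Deaths followed | Difference (points) |
|---|---|---|---|---|---|
| 0.05 | 0.05 | 2 | 90.5% | 90.1% | 0.4 |
| 0.10 | 0.10 | 2 | 81.9% | 80.4% | 1.4 |
| 0.10 | 0.10 | 3 | 81.9% | 79.2% | 2.7 |
| 0.10 | 0.20 | 3 | 81.9% | 76.8% | 5.0 |
| 0.10 | 0.20 | 5 | 81.9% | 73.0% | 8.9 |

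Differences were taken before rounding. At R = 1 the difference is zero throughout. At R = 0.5 the sign reverses and survival is understated by 0.2 to 1.5 points.

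The middle case was also simulated with 70 patients, follow-up uniform over 9 to 33 months and 4,000 runs. That range is the time from diagnosis on 1 January 2025 or 1 January 2023 to the cut-off; follow-up from tafamidis start would be somewhat shorter. The mean 24-month estimates were 81.8% and 79.2%, and about 2.5 of 12.8 deaths fell after stopping and were lost.

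**The case against.** The strongest reply is that the on-treatment window is declared. The objective says so, and the capture rule in section 8.2 matches it. Section 8.9 adds that patients who did not complete treatment may be under-represented and disclaims causal conclusions. This stands in large part: a reader might infer that the restriction is hidden, and it is not. What remains is that section 8.7 drops the qualifier and treats the censoring as properly handled.

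A reader might also infer that survival is shown to be overstated. The documents do not support that. They give no mortality before or after stopping, and the bias vanishes or reverses if risk after stopping is equal or lower. Leaving aside death and loss to follow-up, the only specific entry in "Tafamidis discontinuation reason (1. Mortality, 2. Reimbursement rule, 3. Lost to follow up, 4. other") is a reimbursement rule, and nothing says whether that tracks prognosis.

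Three further inferences fail.

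- Ignoring competing risks is not an error here, because nothing competes with all-cause death.
- Listing mortality as a discontinuation reason does not hide deaths, because Table 1 has a separate all-cause mortality variable with its date.
- A biased primary rate is not established. Section 8.2 follows events already under way to their end, so an admission that begins on treatment and leads to an interruption is counted. Only later events are lost, together with their person-time. That clause does not provide for deaths after discharge.

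Precision is also limited. With 70 patients and survival of 82%, the simple binomial standard error is √(0.82 × 0.18 / 70) = 4.6 points, a 95% half-width of about 9 points. Every gap in the table lies within that. Imprecision does not excuse an avoidable bias, but it does bear on priority.

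**Conclusion.** The point holds in a limited form. As written, the plan yields survival while on tafamidis, with patients censored at a stop or at a gap of 10 days or more. Calling this overall survival in section 8.7 does not match the data collected. As an estimate of overall survival it is likely too high if mortality is higher after stopping, which is plausible but not documented.

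Under the assumed rates the 24-month overstatement is about 0.4 to 9 points; with equal hazards it is zero. The size is illustrative only. The ambiguity in the end-of-exposure date is a lesser matter, but it also reaches the person-years of the primary rate. For a descriptive secondary endpoint this is something the sponsor should fix, not a defect that invalidates the study.

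**What to change.** - For overall survival, abstract vital status and date of death from the available records to 30-Sep-2025, or to last contact if earlier, whatever the tafamidis status. Censor only at those dates.
- Keep the exposure-period estimate that section 7 asks for, label it on-treatment survival, state its censoring assumption, and report discontinuations by reason.
- Reconcile the 10-day definition in section 8.1 with the end date and the cessation wording in Table 1, so that each patient has one end-of-exposure date for the person-years in the primary rate. Which definition applies is for the sponsor to settle.

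The cost is a protocol amendment and one record check per patient who stopped. Section 5 keeps data collection open until 30 June 2026. Deaths come from this centre's records, so vital status may be incomplete for patients who left its care; the number with unknown status should be reported.

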8.2.1. Inclusion Criteria

Patients must meet all the following inclusion criteria to be eligible for inclusion in the study:

1. ≥ 18 years old at the time of diagnosis of ATTR-CM,
2. Diagnosed with hereditary or wild type ATTR-CM confirmed non-invasively (Tc99m PYP bone scintigraphy and/or SPECT-CT) in Samsun Education and Research Hospital – Cardiology Outpatient Clinic between 1 January 2023 – 1 January 2025,
3. Currently receiving or who have received tafamidis treatment for ATTR-CM,
4. Availability of complete medical records, including baseline clinical characteristics, treatment outcomes, and follow-up data from electronic health record systems of hospital or physical patient files.

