8.5. Study Size

[REDACTED]

Furthermore, to minimize selection bias, all patients diagnosed with ATTR-CM treated with tafamidis in this center and who meet the inclusion criteria will be eligible during the 24 months planned for enrollment procedures and until the target number of enrolled patients is reached according to the planned timeline.

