8.9. Strengths and Limitations of the Research Methods

This study will provide insights into the clinical outcomes of ATTR-CM patients treated with tafamidis in Turkey. This localized focus on a unique population adds to the limited data on regional variations in the disease and treatment outcomes.

This study will have several limitations. Being a single-center study, the findings may not be generalizable to other centers, regions, or healthcare systems with different patient populations and practices. Medical records may have missing or incomplete information (e.g., certain biomarkers, imaging results, or medication adherence data).

Ascertainment of CHF hospitalization will be done by a principle investigator using all available records; potential misclassification of the reasons for hospitalizations is possible. To partially address the issue of misclassification, all CV hospitalizations will be captured and recorded in CRF as well. Emergency admissions for causes other than CHF will not be captured and analyzed. There is a potential, that some of the emergency admissions could be related to cardio-vascular causes, but full verification may not be possible; this will remain a limitation of the current study.

Only patients diagnosed and treated at the single participating center will be included, which could lead to a selection bias. Patients lost to follow-up or those who did not complete tafamidis treatment may not be fully represented.

The design of the study does not include a comparative arm and does not allow for robust causal conclusions related to tafamidis treatment effectiveness or safety.

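### Inclusion criterion 4 requires complete outcome and follow-up records, so read literally it selects the cohort on post-index data and contradicts the protocol's own censoring and missing-data rules

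*Protocol*

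**What the plan says.** Protocol section 8.2.1 opens with "Patients must meet all the following inclusion criteria to be eligible for inclusion in the study", so no criterion is optional. The fourth is "Availability of complete medical records, including baseline clinical characteristics, treatment outcomes, and follow-up data". The abstract repeats it. Neither place says what makes a record complete.

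Section 8.2 fixes the timing: "the 6-month period before the index date when tafamidis is started will be considered as the baseline period". Treatment outcomes and follow-up therefore lie after the index date.

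Other parts of the protocol deal with patients whose information is partial:

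- Section 8.2 ends follow-up at the earliest of discontinuation, death, loss to follow-up or 30 September 2025, and adds "For the patients lost to follow-up, the end of their follow-up period will be the respective date of the last contact".
- Table 1 (section 8.3) records death with its date, and lists mortality and loss to follow-up among the reasons for stopping tafamidis.
- Section 8.7 states "Missing data will not be imputed; all analyses will be based on available data", with missing counts reported. Rates are per patient-year and survival is by Kaplan–Meier with censoring.
- Section 8.2 expects the cohort to represent the source population and that of Turkey.
- Section 8.5 says selection bias is limited by making all patients who meet the criteria eligible, but adds "until the target number of enrolled patients is reached according to the planned timeline".
- Section 8.9 concedes: "Patients lost to follow-up or those who did not complete tafamidis treatment may not be fully represented".

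**The concern.** In a cohort that starts at tafamidis initiation, entry should depend only on what is known by then. If the abstractor must also find full outcome and follow-up data, a thin chart can be left out because of what happened, or was not recorded, after the index date. Patients with short or interrupted follow-up are the ones most exposed to this.

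The primary objective (hospitalizations and emergency admissions for chronic heart failure) and overall survival would both be estimated in the selected group. Eligibility is set in the protocol, so no statistical analysis plan can restore patients who never enter the eCRF.

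**Working it through.** **Text comparison.** The protocol states no event rate, survival figure or expected number of exclusions, and made no formal sample size calculation, so there is no figure to reproduce. The check is whether the rules can all hold together.

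1. Criterion 4 is mandatory and names data that exist only after the index date. As worded, eligibility depends on post-index information.
2. The last-contact rule (8.2), the discontinuation reasons (Table 1), Kaplan–Meier censoring and the available-data rule (8.7) all presuppose patients with truncated follow-up or missing values. A strict reading of criterion 4 can remove such patients.
3. A lenient reading, with the record complete up to the patient's own end of follow-up, would remove much of the conflict, but no section states it. Section 8.6 leans the other way: its automatic eCRF check stops a form with missing data from being submitted.
4. Section 8.5 takes all patients who meet the criteria, which leaves the filter in place.

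**Illustration of size.** Every input is an assumption except the 70, which is the planned approximate sample:

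- Admitted: 70 patients, 1.5 years each (105 patient-years), 0.30 events per patient-year (31.5 events), 12-month survival 92%.
- Left out: m = 3, 7 or 14 patients, 0.5 year each, with event rate RR × 0.30 and 12-month survival s.

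The 1.5 years (18 months) is plausible. From the ends of the diagnosis window (1 January 2025 and 1 January 2023) to 30 September 2025 is about 9 and 33 months.

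Full-cohort rate = (31.5 + m × RR × 0.30 × 0.5) / (105 + 0.5m). Reported/full = 0.30 divided by that, which simplifies to (105 + 0.5m) / (105 + 0.5m × RR), so the assumed 0.30 cancels.

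Full-cohort survival = (70 × 0.92 + m × s) / (70 + m). Bias = 0.92 minus that.

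Worked case, m = 14:

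- RR = 3: (31.5 + 6.3) / (105 + 7) = 0.3375; 0.30 / 0.3375 = 0.889.
- s = 50%: (64.4 + 7) / 84 = 0.850; bias 7.0 points.

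| Left out (m) | Rate ratio, RR = 2 | RR = 3 | RR = 0.5 | Survival bias, s = 75% | s = 50% | s = 100% |
|---|---|---|---|---|---|---|
| 3 | 0.986 | 0.973 | 1.007 | +0.7 points | +1.7 | −0.3 |
| 7 | 0.969 | 0.939 | 1.016 | +1.5 | +3.8 | −0.7 |
| 14 | 0.941 | 0.889 | 1.032 | +2.8 | +7.0 | −1.3 |

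If those left out do worse, the reported rate is about 1 to 11% too low and 12-month survival about 1 to 7 points too high. If they do better, both signs reverse.

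**The case against.** The strongest defence is that the protocol, read as a whole, means to include these patients. Criterion 3 admits people who have received tafamidis in the past. Death is an outcome with a date, loss to follow-up is a recorded reason for stopping, and a chart running to death or last contact can be complete for that patient. The study is descriptive, and section 8.9 already warns of selection bias and under-representation.

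Much of this stands, and it rules out several stronger readings a reader might infer:

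- **That patients who die early or are lost necessarily fail criterion 4.** No section says so. The exclusion is possible under an undefined word, not demonstrated.
- **That the results will look too favourable.** The direction is probable for survival and less certain for the hospitalization rate, because patients admitted often at this hospital may have the fullest charts.
- **That this is immortal-time bias.** Section 8.2.1 sets no minimum follow-up, so no event-free span is required for entry.
- **That the rate could be understated by nearly 30%.** With 20% left out, RR = 3 and equal person-time, reported/full = 1/(0.8 + 0.2 × 3) = 0.714. But equal person-time does not fit patients who leave early. With one third of the person-time it is (0.8 + 0.067)/(0.8 + 0.2) = 0.867, or −13%.
- **That the order of chart review will decide who enters once about 70 are reached.** Part of 8.5 is redacted, the number is approximate, and the amendment table in section 4 gives inclusion of all eligible patients as the reason for raising it.

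The defence does not remove the contradiction. The lenient reading is nowhere written, and section 8.9 neither names criterion 4 as a cause nor gives a direction.

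**Conclusion.** The point holds as a contradiction with a possible selection bias. As worded, criterion 4 makes entry depend on post-index data and cannot be reconciled with the rules in 8.2, Table 1 and 8.7 or with the representativeness statement.

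The effect on the heart failure rate and on survival is probably favourable, but its size and sign rest on how many patients are left out and how they fare, and the protocol gives neither. The 1 to 11% and 1 to 7 point ranges hold only under the stated assumptions.

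This should be fixed. It falls short of a fatal flaw because the study is descriptive, the limitation is partly disclosed, and the other rules suggest that inclusion was intended.

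**What to change.** - **8.2.1 and abstract:** limit criterion 4 to records that document the ATTR-CM diagnosis and the tafamidis index date. Drop the completeness requirement and the references to treatment outcomes and follow-up data.
- **Follow-up and missing values:** include every such patient who meets the other criteria from the index date, ending follow-up at death, discontinuation, last contact or 30 September 2025 as 8.2 already provides. Use available data per variable as 8.7 already provides. Make sure the eCRF check in 8.6 accepts a value declared missing.
- **8.5:** bring the target-number clause into line with the stated intention to include all eligible patients.
- **Reporting:** give the numbers screened, included and excluded, with reasons.

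A narrower option is to keep the criterion but define complete as available from the index date to the patient's own end of follow-up under 8.2. This addresses the concern that admissions elsewhere go unseen in patients with thin charts, but it still ties entry to later records, so the first option is preferable. Either way, the last-contact date must be abstracted accurately, because unobserved time counted as follow-up would itself lower the rate.

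The cost is a short amendment needing ethics approval, a few more charts and more missing values to report. Data collection began on 16 October 2025 and is planned to end on 30 June 2026, so charts already set aside under criterion 4 would need a second look.
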